2.3. Schedule of Assessments

Assessment	Visit 1 Screening Day -30 to Day 0	Visit 2 Baseline Day 1	Visit 3 Follow-Up Day 7	Visit 4 Follow-Up Day 14	Visit 5 End of Study Day 21
Informed Consent	X				
Physical Exam	X				
Medical History and Concomitant Medications	X				
Temperature, blood pressure, heart rate measurements taken	X	X	X		X
Questionnaires administered	X	X	X	X	X
Peak Nasal Inspiratory Flow (PNIF) Assessment		X	X	X	X
Urine Sample Collected (for females of childbearing potential)	X	X	X		X
Blood Draw – study endpoint related		X	X		X
Blood Draw - safety	X				X
Saliva Sample – Amplicon Metagenomics Sequencing		X	X		X
Dispense Study Product		X			
Dispense Study Diary		X			
Calculate Compliance			X		
Collect Unused Study Product (if applicable)					X
Collect Study Diary			X	X	X
Adverse Event Assessment		X	X	X	X
Concomitant Medication Review		X	X	X	X
Study Exit Assessments					X

3. Background

Allergic rhinitis (AR) was described in 1929 as a process which included three cardinal symptoms: sneezing, nasal obstruction, and mucus discharge [1]. AR is clinically defined as a symptomatic disorder of the nose induced by an IgE-mediated inflammation after allergen exposure of the membranes lining the nose. AR is a widely prevalent condition in Canada (20-

25%) [2] and other countries; it is often accompanied with significant physical sequelae and recurrent or persistent morbidities. Increasing literature in animals and humans has implicated changes in the gut microbiome with the development of allergic disease [3]–[7], which were shown to be associated with reduced early microbial exposure [6], [8], [9]. Changes of the nasal [10]–[15] and oral microbiota [16]–[18] were found as well.

Some investigations have shown that the oral administration of probiotics and prebiotics may benefit allergic rhinitis patients [19]–[22]. The local nasal administration of *Lactococcus lactis* NZ9000 can affect the local and systemic immune responses against *Streptococcus pneumonia* [23]. Probiotics seem a promising therapeutic approach for allergic airway diseases, however, clinical benefit of probiotic therapy depends upon numerous factors, such as type of bacterium, dosing regimen, delivery method and other underlying host factors, e.g. the age and diet of the host [22]. Among mechanisms of action underlying modulation of immune responses by microbial species, are reduction of permeability of gut barrier and systemic penetration of antigens [22], [24], generation of pro- and anti-inflammatory cytokines in the gut [25]–[27], and modulation of proliferation of immune cells [22], [28], [29].

AllerPops is Natural Health Product in a lozenge dosage form indicated for the alleviating (seasonal) AR. Immune-mediated disorders such as allergic rhinitis is being linked to reduced early microbial exposure [6], [8], [9], dysbiosis of the gut [6], [7], the nasal [10]–[12] and oral microbiota [16]–[18]. The medicinal ingredient was chosen based on its capability to provide balanced nutritional support to the oral microbiota, and thereby restore its presentation and the normal function. The active ingredient, L-Arginine, 5.04%, is used in the formula with the purpose of reducing the nasal symptoms of allergy.

There will be 2 groups of participants in the study (investigational and control). For the investigational group; the method of use of the lozenge product will include two steps: 1) mechanical cleaning of the mouth, followed by 2) slow consumption of the investigational product with the target of its natural dissolution in the mouth after 60 minutes. The purpose of the first step is to remove the biofilm from the teeth and tongue and to provide an unoccluded surface for targeted bacteria to grow. The purpose of the second step is proposed to provide nutrition to the oral bacteria and thereby to restore their balance.

For the control group, the same investigational product will be administered, however the procedure for use will be modified as follows: There will be no mouth cleaning before the product consumption (No step 1 as mentioned above). The product will be swallowed instead of dissolved in the mouth, in order to reduce its presence in the mouth as much as possible. The purpose of this control group is to support the effect of use of the entire two-step method as compared to the investigational group.

The active ingredient, L-Arginine is known to Health Canada. L-Arginine is listed in the NHPID, and allowed for use in NHPs under proposed here conditions of use. Safety of the of current ingredient combination, while allowed for use separately, will also be tested under proposed conditions of use.

The Rationale for Performing Research:

Increase in immune-mediated conditions [30]–[32](Allergic rhinitis is one of them) and the few medical solutions available (each of which is associated with side effects) prompted this research and clinical study. The medicinal ingredient, L-Arginine, in the formulation of AllerPops is a well-known Natural Health Product Ingredient with history of human use.

4. Study Objectives

Objectives:

Primary Objective: To assess the effectiveness of AllerPops on relieving nasal symptoms compared to the control group in volunteers with seasonal and perennial (or intermittent and persistent) allergic rhinitis during the first 7 days of the 21-day intervention period.

Secondary Objectives:

1. To evaluate the safety of AllerPops administration in volunteers with seasonal/year-long allergies during a 21-day intervention period.
2. To assess the duration of effectiveness of AllerPops in relieving nasal symptoms compared to the control group in volunteers with seasonal/year-long allergies during a 21-day intervention period (exploratory).

3. To evaluate the effect of the AllerPops administration on the oral microbial presentation/microbiota using Amplicon Metagenomics Sequencing test through saliva samples during a 21-day intervention period (exploratory).
4. To evaluate the effect of the AllerPops administration on the IgE (total) blood level during a 21-day intervention period (exploratory).

Endpoints:

Primary Endpoint: The reduction of nasal allergic symptoms during the first 7 days of the 21-day intervention period (once every other day – D1, D3, D5). The reduction of symptoms will be measured using the following assessments.

- Total Nasal Symptoms Score (TNSS) Questionnaire: This assessment will be conducted at the V1, V2, and V3.
- Peak Nasal Inspiratory Flow (PNIF): Measures nasal flow for assessing nasal airway patency. This assessment will be conducted at the baseline D1 and D7.

Secondary Endpoint(s):

1. To evaluate the safety of the AllerPops product during a 21-day intervention period. The safety evaluation will be measured based on the following assessments:
 - a. Safety will be assessed by collecting vital signs, the emergence of adverse events, and clinical chemistry (CBC and a comprehensive safety panel) and PI assessment.
2. The exploratory study of the effect of AllerPops in relieving nasal symptoms compared to the control group during a 21-day intervention period. The reduction of symptoms will be measured based on the following assessments:
 - a. Total Nasal Symptoms Score (TNSS) questionnaire: This will be assessed at D14 (V4) and D21 (V5).
 - b. Peak Nasal Inspiratory Flow (PNIF) measurement: This will be assessed at D14 and D21.
3. The exploratory study of the effect of AllerPops in oral microbial presentation/microbiota through Amplicon Metagenomics Sequencing test which is a rRNA gene sequencing method in saliva. The evaluation will be measured at D1, D7 and D21.
4. The exploratory study of the effect of AllerPops on the IgE (total) blood level through blood samples during a 21-day intervention period. The evaluation will be measured at D1, D7 and D21.

5. Selection of Study Population

5.1. Inclusion Criteria

Participants must meet all of the following criteria to be considered eligible for admission to the study.

1. Participants will be clinically diagnosed with persistent or intermittent allergic rhinitis, according to the Allergic Rhinitis and Its Impact on Asthma (ARIA) classification. The guidelines of Allergic Rhinitis and its Impact on Asthma (ARIA) group, classify intermittent as less than 4 days per week and for less than 4 weeks and persistent as more than 4 days per week or lasting more than 4 weeks regardless of the number of days per week).
2. Male or female seasonal/year-long nasal allergy sufferers (as assessed by a questionnaire at screening) between the ages of 18 and 70.
3. Females who are not of childbearing potential (post-menopausal defined as those with amenorrhea for at least 2 years). Females of childbearing potential should be either sexually inactive (abstinent) for 60 days prior to the first dose of the study, throughout the study and for 30 days after completion of the study, or be using one of the following acceptable methods of birth control:
 - v. Surgically sterile (bilateral tubal-ligation, hysterectomy, bilateral oophorectomy) for at least 90 days prior to the first dose of the study.
 - vi. IUD in place for at least 60 days prior to the first dose of the study, throughout the study and for 30 days after completion of the study.
 - vii. Barrier methods (condom, diaphragm) with spermicide for at least 60 days prior to the first dose of the study, throughout the study and for 30 days after study completion.
 - viii. Hormonal contraceptives for at least 90 days prior to the first dose of the study, throughout the study, and for 30 days after study completion.

*Changes to the method of birth control while participating in the study will be judged by the PI for acceptability.

4. Written informed consent obtained and signed by participant.
5. BMI between 18.5 and 29.9 kg/m², with a stable weight over the last 3 months. (A stable weight is defined as <5% of total body weight change in the last 3 months).
6. Agrees not to use any over the counter, prescription, health supplement or dietary supplement from at least 14 days prior to screening until the end of the study.
7. Agrees to maintain current dietary habits, level of physical activity, occupational and living environment for the trial duration.
8. Does not regularly consume more than 2 standard* alcoholic beverages a day as assessed through verbal confirmation at screening, and agrees not to consume >2 standard* alcoholic beverages per day for the trial duration.
9. Non-smoker within 12 months prior to dosing as assessed by verbal confirmation.

10. Stable medical conditions that do not require medication use routinely and do not affect or involve the immune systems as determined by medical history, physical examination, clinical chemistry performed at screening, and as assessed by the Principal Investigator.
11. Agrees not to use nasal steroid spray from at least 14 days prior to screening until the end of the study.
12. Agrees not to use neti-pot and oil-pulling for at least 7 days prior to screening until the end of the study.
13. .
14. Have access to a microwave.

** A standard alcoholic beverage is defined as 12 ounces of beer, 5 ounces, of wine, or 1.5 ounces of liquor*

5.2 Exclusion Criteria

Participants meeting any of the following criteria will not be eligible for admission to the study:

1. Participants who are pregnant/lactating or planning to become pregnant during the course of the clinical trial.
2. Participants who have any signs of active or recurrent upper airway infection (bacterial/viral).
3. Participants who have a known sensitivity or allergy to any of the study products, or ingredients.
4. Participation in another research study within 30 days prior to enrollment in this clinical trial.
5. Participants who are not able to tolerate venipuncture and/or have poor venous access.
6. Participants dependent on decongestants (nasal or oral) or receiving allergen-specific immunotherapy.
7. Participants who have been diagnosed with other clinical forms of rhinitis such as infectious rhinitis, rhinitis of pregnancy, food and alcohol-induced rhinitis, atrophic rhinitis, vasomotor rhinitis, rhinosinusitis and age-related rhinitis.
8. Participants who have receive previous acupuncture treatment or alternative medicine for AR in the last three months or planned in the next two years.
9. Participants who have received allergy desensitization therapy (current, during the past two years, or planned in the next two years).
10. Participants who have had any major surgery within 1 year of enrollment into the clinical trial or have any anticipated major surgeries intended to occur during the clinical trial.
11. Participants who have received a blood transfusion within 8 weeks of enrollment in the clinical trial.
12. Participants who have donated blood or plasma to a blood bank or clinical study within 8 weeks of enrollment and during the study except venipuncture as part of clinical trial.
13. Participant has known severe medical conditions, such as cardiovascular, liver or renal dysfunction, diabetes mellitus, cancers, cerebrovascular diseases, blood system diseases

which in the opinion of the Principal Investigator, may preclude safe study participation, or interfere with study objectives.

14. Participants who are immunocompromised or have been diagnosed HIV/AIDS, Hepatitis B, or untreated Hepatitis C.
15. Participant has a history of alcohol or drug addiction treatment within the last 2 years prior to inclusion in the study, or any current addiction on alcohol or drugs.
16. Participants with Grade II or III septum deviation and/or presence of nasal polyps or other conditions that lead to nasal obstruction.
17. Participant has any other medical, social or other condition that, in the opinion of the Principal Investigator, would make participation in the study unsafe, complicate interpretation of study outcome data, or otherwise interfere with achieving the study objectives.
18. Participants with allergic asthma and/or moderate to severe atopic dermatitis.
19. History of anaphylactic reactions.
20. Participants with any risk of developing dental cavity or on-going oral health issue, as assessed during their regular dentist visit in past 6 months.
21. Participants who brush more than twice a day and/or mouthwash more than once a day and/or floss more than once a day.

5.3 Concomitant Medications

Apart from the dispensed IP(s), any medication taken by the participant throughout the study period will be regarded as concomitant treatment. During the study, participants shall be instructed not to take medications unless absolutely necessary. If the use of any concomitant treatment becomes necessary during the study, the treatment will be recorded, including the name of the drug or treatment, indication for use, dosage, route, date, and time of treatment.

5.4 Early Withdrawal

Removal of Study Participants:

The removal of a study participant will be based on the Clinical, and Protocol Violation conditions outlined below. If possible, any evaluations or assessments planned for the end of the study will be completed at an Early Termination (ET) Visit. Criteria for participant removal at the PI's discretion are:

Removal by Principal Investigator

The removal of a study participant by the principal investigator will be based on the Clinical and Protocol Violation conditions outlined below. If possible, any evaluations or assessments planned for the end of the study will be completed at an Early Termination (ET) Visit. Criteria for participant removal at the PI's discretion are:

Clinical

A participant may be withdrawn from the study if, in the opinion of the PI, it is not in the best interest of the participant to continue. Participants who experience an adverse event (AE) or

severe adverse event (SAE) will be assessed by the PI and determine if removal from the study is necessary. Participants experiencing a SAE will be followed up by PI until resolution of SAE. Any female who becomes pregnant during the course of the study will be removed and followed-up with accordingly.

Protocol Violation

Protocol violations may be a result of the above inclusion/exclusion criteria. Violations will be assessed by the PI on a case-by-case basis with removal from the study, if necessary. Participants can be withdrawn from the study at the discretion of the Sponsor. Participants who are deemed to be a protocol violation will not be followed up on.

6. Investigational Product

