11.2. Study Population

Intention-to-treat (ITT) analysis will be considered in this study. ITT analysis includes every subject who is randomized according to randomized treatment assignment. The ITT analysis includes all randomized patients in the groups to which they were randomly assigned, regardless of their adherence with the entry criteria, regardless of the treatment they actually received, and regardless of subsequent withdrawal from treatment or deviation from the protocol. ITT analysis reflects the practical clinical scenario because it admits noncompliance and protocol deviations. ITT analysis maintains prognostic balance generated from the original random treatment allocation and it gives an unbiased estimate of treatment effect.

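### Section 5.4 ends follow-up of protocol violators whom section 11.2 keeps in the ITT analysis, so a violator removed before Day 7 could lack the primary TNSS and PNIF

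*Combined protocol and SAP*

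**What the plan says.** Section 5.4 sets out removal under two headings, Clinical and Protocol Violation. Its lead-in applies to both: "If possible, any evaluations or assessments planned for the end of the study will be completed at an Early Termination (ET) Visit". Under Protocol Violation it says "Protocol violations may be a result of the above inclusion/exclusion criteria", leaves removal to the PI case by case, adds "Participants can be withdrawn from the study at the discretion of the Sponsor", and closes with "Participants who are deemed to be a protocol violation will not be followed up on".

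Section 11.2 defines the analysis population as everyone randomised, in the assigned arm, "regardless of their adherence with the entry criteria" and "regardless of subsequent withdrawal from treatment or deviation from the protocol". It says of this analysis that "it gives an unbiased estimate of treatment effect".

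Section 11.3.1 builds both primary variables on the change from Day 1 to Day 7, in TNSS and in PNIF. Section 8 places the Day 7 visit (Visit 3) in a window of ± 1 day.

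**The concern.** An ITT rule fixes who is analysed and in which arm. It cannot supply an outcome that nobody collected. On its plain wording, the last sentence of 5.4 stops contact with people whom 11.2 undertakes to analyse, and it does so for the very group, entry-criteria breaches, that 11.2 says must stay in.

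The stake is the Day 7 TNSS and PNIF of a participant deemed a violator and removed before Visit 3. Those values cannot be recovered later. Because removal is a judgement by the PI or the Sponsor, the participants lost need not be a random subset, and the claim of an unbiased estimate would then no longer follow from randomisation alone.

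**Working it through.** **1. Side by side.**

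| Question | Section 5.4 | Section 11.2 |
|---|---|---|
| Entry-criteria breach found after randomisation | May be a violation; no follow-up | Analysed |
| Removed for a violation | Early Termination visit where possible; no follow-up | Analysed |
| Day 7 outcome secured? | Not stated | Assumed by the primary analysis |

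**2. Does the Early Termination visit fill the gap?** In part. It covers violators, and the end-of-study assessments listed for Visit 5 include TNSS and PNIF. It is conditional, however, and not tied to Day 7 ± 1. The TNSS in Appendix 1 asks about the past week, so timing matters. Suppose that means the 7 days before the visit, with the first dose on Day 1. A score on Day 4 (a hypothetical date) then covers Days -3 to 3, of which 4 of 7 precede Day 1. A score on Day 7 covers Days 0 to 6, of which 1 of 7 does.

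**3. How many could be affected before Day 7?** The documents give no violation rate. Their schedule suggests few:
- Eligibility is confirmed before allocation (6.5).
- No visit falls between Day 1 and Day 7 (2.3).
- The diary is first reviewed at Visit 3 (8), and the compliance calculation applies only to Visit 3 (9.8). The primary TNSS and PNIF are taken at that visit.
- Visit 2 information is reviewed before the next visit (8), so an earlier removal is possible, though that review concerns safe participation.

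After Day 7, efficacy is exploratory (4, 11.3.3).

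**4. Illustration of size.** The plan states no figure for violations or missing outcomes. Its only relevant number is 72 participants (11.1), allocated equally (6.6): 72/2 = 36 per arm. Everything else is assumed: no true effect, k = 1 to 3 participants lost from one arm only, and a latent removal propensity correlated r = 0.3 to 0.5 with poor response.

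Let f = k/36, z the upper-f point of the standard normal, and φ the normal density at z.
- Shift in that arm's mean, in SD units: r·φ/(1 − f).
- How much worse than their arm the removed participants are: r·φ/f.

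| k | f | φ | Shift, r = 0.3 / 0.5 | Removed worse by (SD), r = 0.3 / 0.5 |
|---|---|---|---|---|
| 1 | 0.028 | 0.064 | 0.020 / 0.033 | 0.69 / 1.15 |
| 2 | 0.056 | 0.112 | 0.036 / 0.059 | 0.61 / 1.01 |
| 3 | 0.083 | 0.153 | 0.050 / 0.084 | 0.55 / 0.92 |

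For k = 3 and r = 0.5: 0.5 × 0.153/(1 − 0.083) = 0.084. Simulation with 100,000 trials per case, removing exactly k of 36, gave 0.019 to 0.081. If both arms lose the same number in the same way, the two shifts cancel and the expected difference is zero.

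**5. Why the size is given in SD.** Turning the shift into a false-positive rate requires the sidedness of the test, which the readable text of 11.1 does not state. By noncentral t (36 against 36 − k, α = 0.05), a two-sided test gives 5.1 to 6.4%. A one-sided test gives 5.9 to 9.7% if the shift favours the tested direction and 2.3 to 4.2% if it opposes it.

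**The case against.** The strongest reply is that 5.4 and 11.2 do different jobs: one governs conduct after a violation, the other says who is analysed. An ITT set with a few missing outcomes is incomplete, not contradictory. That is fair as logic, but the plan also claims an unbiased estimate, and that claim needs the outcomes.

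Several stronger readings are tempting, and the documents do not support them.

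- *That 5.4 contradicts itself by offering an Early Termination visit and then forbidding follow-up.* The two can run in sequence: removal, a visit if possible, then nothing further. What stands is that this visit does not secure a Day 7 value.
- *That the sentence plainly bars all outcome collection.* The preceding paragraph uses the same verb for safety: "Participants experiencing a SAE will be followed up by PI until resolution of SAE". The sentence may have been meant in that sense. It does not say so, and site staff could act on either reading.
- *That non-compliance and other conduct deviations also lose follow-up.* Section 12 allows some deviations to be classed as violations, but it deals with filing and reporting and mentions neither removal nor follow-up. The extension is inference.
- *That the primary result is materially biased.* The documents give no rate, direction or imbalance between arms. The illustration puts all the loss in one arm by assumption.

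Section 11 also gives no method for missing outcomes. That applies to every dropout and would remain however 5.4 is worded, so it is not what this point rests on.

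**Conclusion.** The point holds as a minor one. As written, 5.4 permits a site to stop collecting outcomes from people whom 11.2 includes, and the Early Termination visit does not guarantee the primary Day 7 values. The number affected is unknown and probably small, because the schedule brings most breaches to light before allocation or at Visit 3 itself.

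Any bias requires loss that is both related to response and unequal between arms. If 1 to 3 of 36 were lost from one arm under the correlations assumed above, the between-arm difference would move by about 0.02 to 0.08 SD. That range gives a sense of scale and is not an estimate for this trial.

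**What to change.** Reconcile 5.4 with 11.2 by replacing the no-follow-up sentence with a data-collection statement along these lines: a protocol violation, or removal for one by the PI or Sponsor, does not by itself end outcome data collection; the scheduled TNSS and PNIF assessments, at least those at Day 7, are still completed unless the participant withdraws consent or is withdrawn under the Clinical provisions.

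Leave the removal, clinical and safety follow-up provisions as they are. If the sentence was meant only for safety follow-up, say so separately; this point takes no position on that.

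The cost is amendment wording, plus a few more participants attending visits that are already scheduled.

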 - Serum creatinine
 - Potassium
 - Chloride
 - Sodium
 - IgE (total)
8. Be provided with a paper/electronic diary – IP dosing, adverse events, concomitant medication.
9. Be provided with the IP (and oral hygiene kit if applicable) and instructions on dosing.
10. Be provided with dates/times of subsequent visit(s).
11. Review of all information for the visit by the PI and/or delegate prior to the next study visit to determine continued safe participation.

The participant will be given a paper/electronic daily diary in order to record the use of concomitant medications, IP dosing, symptoms, and any adverse events (such as fatigue, fever or headache) that may have occurred. The diary will be collected and/or reviewed at the research site at each visit as indicated on the Schedule of Assessments.

The participant should take the IP after this visit at home. The participant should take AllerPops at a maximum frequency of once every other day until the next study visit (Day 7). The participant should not take the product the morning of the next visit. The designated maximum dose until the next visit on day 7, is 3 doses.

Visit 3 – Follow-Up – Day 7 ± 1

These assessments may not be completed in the order shown below.

Participants:

1. Must be at least 8 hours fasting (no food, only water) prior to visit.
2. Will have any changes to health reviewed by delegated study staff.
3. Study diary will be collected and/or reviewed by delegated study staff for completion, and any AEs and/or concomitant medications.
4. For females of childbearing potential, a urine sample will be collected for a urine pregnancy test.

5. Will have the following measurements taken: temperature, blood pressure, heart rate.
6. Will have the following saliva test:
 - Amplicon Metagenomics Sequencing
7. Will complete the following assessments:
 - Total nasal symptoms score (TNSS) questionnaire
 - Peak nasal inspiratory flow (PNIF) measurement
8. Will have the following blood tests:
 - CBC (WBC, RBC, Hb, HCT, MCV, MCH, MCHC, Platelet Count)
 - Aspartate aminotransferase (AST)
 - Alanine aminotransferase (ALT)
 - Bilirubin
 - Gamma-glutamyl transferase (GGT)
 - Alkaline phosphatase (ALP)
 - Serum creatinine
 - Potassium
 - Chloride
 - Sodium
 - IgE (total)
9. Be reminded to complete daily diary.
10. Review of all information for the visit by the PI and/or delegate prior to the next study visit to determine continued safe participation.

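### Section 5.4 can be read as ending outcome collection for protocol violators whom the ITT analysis in 11.2 keeps; mainly Day 14 and Day 21 data are exposed

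*Combined protocol and SAP*

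**What the plan says.** **Follow-up.** Section 5.4 (Early Withdrawal), under Protocol Violation, leaves removal to the PI: "Violations will be assessed by the PI on a case-by-case basis with removal from the study, if necessary". It closes with "Participants who are deemed to be a protocol violation will not be followed up on". That sentence is not limited to participants who are removed, nor to any one kind of follow-up. Earlier in 5.4, for removals on clinical or violation grounds, the plan says: "If possible, any evaluations or assessments planned for the end of the study will be completed at an Early Termination (ET) Visit".

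**Analysis.** Section 11.2 adopts ITT for all randomised participants, whether or not they met the entry criteria and "regardless of subsequent withdrawal from treatment or deviation from the protocol". Sections 11.1 and 11.3 name t tests, non-parametric alternatives, transformations and exploratory data analysis. They give no imputation, longitudinal model or sensitivity analysis, and no rule for placing ET values.

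**Timing.** Under section 4, the primary TNSS and PNIF comparison ends at Day 7 (Visit 3). TNSS and PNIF at Days 14 and 21 are exploratory. Safety over 21 days is the only secondary objective not marked exploratory.

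**The concern.** The participants whom 5.4 stops following are among those whom 11.2 undertakes to analyse. A two-sample test can use only the values it has, so without their outcomes the ITT analysis becomes an analysis of whoever remained under observation. Section 11.2 says that ITT gives an unbiased estimate, and that depends on having those outcomes.

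Whether someone is deemed a violation is a PI judgement made after randomisation, so the loss could be related to outcome. Data never collected cannot be recovered at analysis. The data at stake are chiefly those for duration of effect and for end-of-study safety, and under narrower conditions the primary Day 7 values.

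**Working it through.** **1. The two rules side by side**

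| Participant | 5.4, read literally | 11.2 |
|---|---|---|
| Randomised, later found ineligible, deemed a violation | Not followed; ET visit if removed and if possible | Analysed as randomised |
| Other violation, removed by the PI | Not followed; ET visit if possible | Analysed as randomised |
| Violation, not removed | Not followed, although still in the study | Analysed as randomised |

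In the third row the literal reading fits poorly with case-by-case removal, so the wording needs settling either way.

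**2. What the ET visit recovers.** It covers end-of-study assessments, which at Visit 5 include TNSS, PNIF and safety bloods. It gives one set of values at an unscheduled time. Section 11 does not say whether these stand for Day 7, 14 or 21, or are left out.

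**3. When a violation is found decides what is lost** (section 8)

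- *Between Day 1 and Visit 3.* No participant contact is scheduled. Visit 2 does end with "Review of all information for the visit by the PI and/or delegate prior to the next study visit to determine continued safe participation", and unscheduled contact or an electronic diary might also reveal something. A participant dropped here loses Day 7, 14 and 21 values.
- *At Visit 3.* The list puts diary review ("Study diary will be collected and/or reviewed by delegated study staff for completion, and any AEs and/or concomitant medications") at item 3 and TNSS and PNIF at item 7, but "These assessments may not be completed in the order shown below". Day 7 is lost only if the visit is stopped before item 7 is done.
- *After the Visit 3 TNSS and PNIF.* The primary data are already in hand. The exposure is Day 14 and Day 21 TNSS and PNIF, and Day 21 safety.

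**4. The plan's sample size.** Inputs from 11.1: effect size 0.6, 80% power, significance at 0.05, two independent means, 72 participants. Section 6.6 gives equal groups, so 72 / 2 = 36 per arm. The readable text does not state sidedness, so both are shown. Solving the noncentral t for 80% power:

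- one-sided: 35.04, rounded up to 36 per arm, 72 in total, which reproduces the plan's figure;
- two-sided: 44.59, rounded up to 45 per arm, 90 in total, which does not.

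**5. Power if Day 7 values are lost.** The documents give no rate of violations, so losses of 1 to 3 are assumptions. Power is the probability that a noncentral t variable with df = n1 + n2 − 2 and noncentrality 0.6 × √(n1·n2/(n1 + n2)) passes the critical value. For 36/36 the noncentrality is 0.6 × √18 = 2.546 with 70 df.

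| Day 7 values per arm | Noncentrality | One-sided 0.05 | Two-sided 0.05 |
|---|---|---|---|
| 36 / 36 (no loss) | 2.546 | 80.9% | 70.9% |
| 35 / 35 | 2.510 | 80.0% | 69.7% |
| 33 / 33 | 2.437 | 77.8% | 67.0% |
| 36 / 35 (one arm only) | 2.528 | 80.5% | 70.3% |
| 36 / 33 (one arm only) | 2.490 | 79.4% | 68.9% |

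The largest drop is 80.9 − 77.8 = 3.1 points one-sided and 70.9 − 67.0 = 3.9 points two-sided. If losses are confined to Days 14 and 21, primary power does not change.

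**The case against.** The best defence is that the sentence concerns clinical follow-up. The text just before it in 5.4 speaks of following SAEs to resolution and following up pregnancies, and the ET provision and case-by-case removal would have little purpose if every violator simply disappeared from data collection. This reading is at least as natural as the literal one, and it stands as a reason to call the sentence ambiguous. It does not remove the problem: the sentence carries no such limit, and a site could reasonably stop all visits on the strength of it.

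It is also fair that eligibility is confirmed before allocation (6.5), that the review after Visit 2 is framed as a safety check, that nothing tells staff to halt Visit 3 before the outcome measures, and that the Day 14 and 21 efficacy data are exploratory. These points limit the weight of the concern.

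Three stronger readings are tempting, and the documents do not support them.

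- *One missed dose leads to lost data.* A reader might infer this because "The designated maximum dose until the next visit on day 7, is 3 doses", so that two doses give 2/3 = 66.7%, outside the 80–120% band in 9.8. But 9.8 calls that a deviation, and only when product is returned, which the visit text places at Visit 4. Reclassification as a violation under section 12 is then optional. Too many discretionary steps separate the missed dose from a lost value.
- *The primary result is compromised.* Day 7 loss needs a violation to be both found and acted on before the Visit 3 TNSS and PNIF, which is the less likely case.
- *Violations will differ by arm.* The arms follow different home procedures, so this is possible, but nothing in the documents shows it.

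**Conclusion.** The concern holds in limited form. Sections 5.4 and 11.2 conflict on a literal reading, and section 11 has nothing that repairs the conflict. The likelier loss is Day 14 and Day 21 TNSS and PNIF, which carry the exploratory duration-of-effect objective, together with Day 21 safety data. Primary Day 7 data are at risk only in the narrow window described.

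The number of violators, and the size and direction of any bias, cannot be estimated from the documents. Under assumed losses of up to 3 Day 7 values per arm the power cost is below 4 points. What matters is selective loss, rather than power. That most violations would surface at or after Visit 3 is inferred from the visit schedule; the documents give no counts. The change is worth making because the wording invites avoidable loss and is cheap to correct. Confidence is medium, since the sponsor may have intended clinical follow-up only.

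**What to change.** In 5.4, replace the sentence on violators with:

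> A protocol violation, or removal from study product, does not end data collection: the remaining scheduled TNSS, PNIF and safety assessments (Days 7, 14 and 21) are obtained, safety and consent permitting, and analysed under ITT; the ET visit is used only when a participant will not attend the remaining visits.

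The last clause reconciles the new text with the two ET statements in 5.4. In 11.3, add a table by arm giving the number of violators and of missing TNSS and PNIF values at Days 7, 14 and 21.

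**Cost.** Both edits need a protocol amendment with regulatory approval under section 13. No visit is added to the schedule, but removed participants would be asked to attend those that remain. Values taken after a violation stay in the ITT comparison and may dilute a difference between arms. That consequence already follows from the choice of ITT in 11.2.
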